### Bile acid and Gut microbiota

BA are essential molecules in fat absorption by acting as a surfactant that emulsifies them into micelles (3). It is well established that the majority of patients with FD report onset or worsening of symptoms after a meal, which coincides with the release of BA into the duodenum (4). Furthermore, we proved that patients with FD are characterized by a decreased duodenal BA concentration in fasted state compared to healthy volunteers (2).

Another important feature of bile acids is their strong antimicrobial activity. In fact, oral administration of bile acid regulates the composition of gut microbiota in rats (5). The gut microbiota maintains a symbiotic relationship with the host and regulates several important functions including host metabolism, immunity, and intestinal barrier function. Intestinal inflammation is commonly associated with dysbiosis of the gut microbiota (6). Duodenal inflammation has been observed in up to 40% of patients with FD and, hence, it is thought to be an important factor in the pathogenesis of FD (7). A decreased duodenal BA might play a role in duodenal inflammation via duodenal dysbiosis in the pathophysiology of FD, while it is not well proven the relationship between the pathogenesis of FD and BA (2).

### Gastric sensorimotor function

Impaired gastric sensorimotor function, such as decreased gastric accommodation, delayed gastric emptying and gastric hypersensitivity, has been implicated in symptom generation in FD (8). These alterations may represent new targets for therapy (e.g. improving gastric accommodation). We have already established a new minimally invasive technique that measures the intragastric pressure (IGP) drop during a liquid meal challenge as a method to assess gastric accommodation in FD patient (9, 10).

The migrating motor complex (MMC) is a cyclic motor pattern in the gastrointestinal tract that occurs during the interdigestive state and is responsible for the rumbling experience when hungry (11). Its absence has been associated with FD, gastroparesis and small intestinal bacterial overgrowth (11). IGP and MMC techniques use the same catheter as in esophageal high-resolution manometry and, therefore, have the potential to gain a similar acceptance and feasibility level for clinical routine diagnostic test.

### Gastrointestinal hormones

The gastrointestinal (GI) hormones constitute a group of hormones secreted by enteroendocrine cells in the stomach, pancreas, and small intestine that control various functions of the digestive organs, including gastric motility. Motilin and ghrelin are the GI hormones released in a fasting state to stimulate the GI motility of the MMC (12). Recent research has shown that both the MMC and motilin play a role in hunger signaling and changes in both occur in food intake disorders (13). Glucagon-like peptide-1 and 2 (GLP-1, GLP-2) inhibits gastric emptying with secondary effects on the release of insulin in fed state (14, 15). BA stimulate GLP-1, GLP-2 and insulin (16, 17).

### Farnesoid X receptor (FXR) agonist

Farnesoid X receptor (FXR) is a bile acid receptor, which is mainly expressed in the liver and intestine. FXR regulates synthesis, secretion and transport of bile acids (18). It has been considered as a promising target for the treatment of cholestatic disorders, including primary biliary cirrhosis (PBC) (19). FXR is also important for the regulation of the lipid and glucose metabolism (18). The activation of FXR showed beneficial effects on various metabolic diseases, including fatty liver diseases, type 2 diabetes, dyslipidemia, and obesity (18). Obeticholic acid (OCA), a FXR agonist, is proven as an effective drug for PBC (19). In 2016, OCA was approved in U.S. and Europe for the treatment of PBC. OCA is used together with another

medicine, ursodeoxycholic acid (UDCA), in patients who do not respond sufficiently to UDCA alone, and on its own in patients who cannot take UDCA. Now, phase III study for NASH is ongoing. In healthy volunteers, patients with primary biliary cholangitis (PBC) and patients with non-alcoholic steatohepatitis (NASH), single and multiple doses of obeticholic acid were well tolerated (19, 20). The most frequently reported adverse events considered to be drug-related were pruritus and fatigue (19, 20). Some abdominal pain and discomfort were reported. Based on a multiple-center phase III study in PBC patients, the recommended starting dosage of OCA is 5 mg orally once daily for 3 months with titration to 10 mg once daily based upon tolerability and response(21). In conclusion, obeticholic acid was found to be safe.

Recently, Friedman ES et al showed alteration of gut microbiome by OCA. In this study, male C57BL/6 mice were gavaged daily with water, vehicle, or OCA (10 mg/kg) for 2 weeks. Small intestine luminal contents were collected by flushing with saline and fecal pellets were collected at baseline and day 14. Culture experiments were performed to determine taxonomic-specific effects of bile acids and OCA on bacterial growth. As a result, administration of OCA dramatically led lower endogenous bile acid levels and an increased proportion of Firmicutes, specifically in the small intestine but not in stool, compared to control in mice (22). Friedman ES et al also conducted healthy volunteers on OCA doses of 5, 10 or 25mg/d and analyzed their microbiome in stool (22), however it is still unclear how the intestinal microbiome changes in human.

OCA might alter the gut microbiota and duodenal inflammation. Moreover, gastric motility, accommodation and gastrointestinal peptide might be affected through the change of duodenal circumstance. Therefore, the aim of the current research protocol is to investigate the relationship between FXR agonist and gut microbiota, gastric motility, accommodation, gastrointestinal peptide in healthy volunteers.

## 2 Trial Objectives and Design

### 2.1 Trial objectives

The aim of this study is to investigate the effect of OCA (FXR agonist) on gut microbiota, gastric motility, gastrointestinal peptide in healthy individuals.

### 2.2 Primary Endpoints

*The primary endpoint of this study is to compare appetite/hunger between placebo and treatment with OCA .*

### 2.3 Secondary Endpoints

The secondary endpoint is to compare gastric motility, the distribution of gut microbiota and BA composition between placebo and treatment with OCA .

Gastric motility and the release of the hormones motilin, ghrelin, GLP-1, GLP-2, GIP and insulin will be compared between placebo and treatment with OCA .

### 2.4 Trial Design

This study is a single-blind, placebo-controlled, randomized, study in healthy individuals.

### 2.5 Expected Duration of the Trial

01/10/2021-31/12/2022

## 3 Trial Population / Eligibility Criteria

### 3.1 Inclusion criteria

Participants eligible for inclusion in this Trial must meet **all** of the following criteria:

- I. Voluntary written informed consent of the participant or their legally authorized representative has been obtained prior to any screening procedures

2. Use of highly effective methods of birth control; defined as those that, alone or in combination, result in low failure rate (i.e., less than 1% per year) when used consistently and correctly; such as implants, injectables, combined oral contraceptives, some IUDs, true sexual abstinence (i.e. refraining from heterosexual intercourse during the entire period of risk associated with the Trial treatment(s)) or commitment to a vasectomised partner.
3. Subject is between 18 and 65 years of age
4. Subject has a BMI between 18 and 25 kg/m^2

All participants that are considered for Trial participation, per the above criteria will be documented on the Screening Log, including Screen Failures.

### 3.2 Exclusion criteria

Participants eligible for this Trial must not meet any of the following criteria:

1. Participant has a history of gastrointestinal or other significant somatic or psychiatric diseases or drug allergies, diabetes, a significant heart, lung, liver or kidney disease, a neurological disorder, abdominal surgery (including gallbladder removal, but those having undergone a simple appendectomy more than 1 year prior to the screening visit may participate),
2. Any disorder, which in the Investigator's opinion might jeopardise the participant's safety or compliance with the protocol
3. Any prior or concomitant treatment(s) that might jeopardise the participant's safety or that would compromise the integrity of the Trial
4. Female who is pregnant, breast-feeding or intends to become pregnant or is of child-bearing potential and not using an adequate, highly effective contraceptive
5. Participation in an interventional Trial with an investigational medicinal product (IMP) or device
6. High caffeine intake (> 500 ml coffee daily or equivalent).
7. Subject consumes excessive amounts of alcohol, defined as >21 units per week for men, >14 units per week for women.
8. Subject is currently (defined as within approximately 1 year of the screening visit) a regular or irregular user (including "recreational use") of any illicit drugs (including marijuana) or has a history of drug (including alcohol) abuse. Further, patient is unwilling to refrain from the use of drugs during this study.
9. Inability or unwillingness to perform all of the study procedures, or the subject is considered unsuitable in any way by the principal investigator.
10. Recent participation (<30 days) or simultaneous participation in another clinical study.
11. Prior participation in a clinical trial of obeticholic acid

Participants who meet one or more of the above exclusion criteria **must not proceed** to be enrolled/randomized in the Trial and will be identified on the Screening Log as Screen Failure.

## 4 Trial Procedures

### 4.1 Participant consent and withdrawal of consent

The Trial will be conducted only on the basis of prior informed consent by the Trial participants and/or their legally authorized representative(s). As such, no Trial-related procedures will be conducted prior to obtaining written informed consent from potential Trial participants.

The process for obtaining and documenting initial and continued informed consent from potential Trial participants will be conducted in accordance with ICH-GCP E6(R2), applicable regulatory requirements and internal Standard Operating Procedures (SOPs).

All originally signed obtained Informed Consent Forms (ICFs) must be retained/archived in the Investigator Site File (ISF) at the Participating Site and must not be destroyed (even when a scanned copy is available) before expiration of the legal archiving term as defined in the protocol section entitled "Archiving".

Participants may voluntarily withdraw consent to participate in the Trial for any reason at any time. The participant's request to withdraw from the Trial must always be respected without prejudice or consequence to further treatment. Consent withdrawal will be documented in the participant's medical record.

Trial data and samples collected before withdrawal can be used in the trial. No new trial data or samples will be collected after withdrawal of the participant.

#### **4.2 Selection of Participants / Recruitment**

Potential subjects will be recruited by means of an existing volunteer database from the research group of the Sponsor-Investigator. Potential subject will be contacted by phone or per email with a short introduction on the study purpose and the proposal to make an appointment if they are interested in participating, through oral advertisement and through advertisement on the UZ Leuven intranet and on notice boards of the KU Leuven.

#### **4.3 Randomization Procedure / Blinding (if applicable)**

##### Randomization

To ensure the integrity of the Trial, the following randomization procedures have been established:

A randomization online software (<http://www.randomization.com>) will be used to generate randomization plan.

A randomization list will be prepared by the Sponsor's designated staff, not involved in recruiting Trial participants, medical care, drug administration or follow-up.

##### Blinding

To avoid bias, treatment arms will be blinded to the Drug provider, as follows:

The IMP will be manufactured, packaged and labelled in such a way that the visual appearance, nor the smell and/or touch of the IMP can be distinguished from the comparator treatment and/or placebo.

Furthermore, to maintain the blind, the IMP and any comparator treatment(s) and/or placebo will follow the same administration route and process.

#### **4.4 Unblinding**

After all participants have completed the Trial, the database will be locked and the collected Trial data will be unblinded to allow analysis of the Trial data.

In case of an emergency in a blinded Trial, the Investigator has the sole responsibility for determining if premature unblinding of a participant's treatment assignment is warranted. Participant safety must always be the first consideration in making such a determination. Every effort should be made to contact the Sponsor prior to unblinding a participant's treatment assignment, unless this would delay emergency treatment of the participant. The Sponsor must be notified as soon as possible and no later than within 24 hours after breaking the blind. The date and reason for unblinding must be recorded in the source documentation and electronic Case Report Form (eCRF), as applicable.

#### **4.5 Premature discontinuation of Trial treatment**

Participants may voluntarily discontinue from Trial treatment and/or prematurely end their participation in the Trial for any reason at any time. In such case the Investigator must make a reasonable effort to contact the participant (e.g. via telephone, e-mail, letter) in order to document the primary reason for this decision.

The Investigator may also decide at any time during the course of the Trial, to temporarily interrupt or permanently discontinue the Trial treatment if it is deemed that continuation would be detrimental to, or not in the best interest of the participant.

Similarly, de Sponsor, Ethics Committee or authorized regulatory authority can decide to halt or prematurely terminate the Trial when new information becomes available whereby the rights, safety and well-being of Trial participants can no longer be assured, when de integrity of the Trial has been compromised, or when the scientific value of the Trial becomes obsolete and/or unjustifiable.

Circumstances requiring premature treatment interruption or discontinuation of the Trial, include but are not limited to:

- Safety concerns related to IMP or unacceptable intolerance
- Trial participation while in violation of the inclusion and/or exclusion criteria
- Pregnancy
- Intention of becoming pregnant

In any such case of early Trial termination and/or treatment interruption/discontinuation, the Investigator will continue to closely monitor the participant's condition and ensure adequate medical care and follow-up. It is recommended that follow-up information will be collected as follows:

The Investigator will assess physical damage at the end of treatment and provide medical care and follow-up as necessary

For participants whose status is unclear because they fail to appear for Trial visits without stating an intention to discontinue or withdraw, the Investigator must make every effort to demonstrate "due diligence" by documenting in the source documents which steps have been taken to contact the participant to clarify their willingness and ability to continue their participation in the Trial (e.g. dates of telephone calls, registered letters, etc.).

[figure not shown]
A participant should not be considered lost to follow-up until due diligence has been completed.

## 5 Trial Medication / Drug

Generic Drug Name (& company brand name)	IMP or non-IMP	Used within Indication? (Y or N)	Route of administration (po,sc,iv,...)	Dose/dosage and units
Obeticholic acid (OCALIVA®)	IMP	N	po	10 mg
Placebo	IMP	N	po	placebo

### 5.1 Investigational Medicinal Product and Dosing Regimen

In this study, participants will receive in total one dose of OCA (OCALIVA®, Intercept Pharmaceuticals, New York, United States) and one dose of placebo (Intercept Pharmaceuticals, New York, United States) in a phase II, single-blind, randomized crossover fashion.

One dose of study medication consists of 1 tablet (10mg) of placebo or OCA. OCA and placebo will be orally administered with water in the morning for 21 days after the examinations at preintervention.

OCALIVA® is a drug which is only available on prescription, it is indicated for the treatment of primary biliary cholangitis (ATC code A05AA04). OCALIVA® tablets contain 10 mg obeticholic acid and 176 mg Microcrystalline cellulose, 12 mg Sodium starch glycolate, 2 mg Magnesium stearate, tablets are film coated and dissolve in the acidic environment of the stomach. One dose of study medication will contain 10 mg obeticholic acid.

Placebo tablets will be obtained from Intercept Pharmaceuticals, New York, United States and will contain 320 mg lactose monohydrate, 10 mg carmellose sodium, 70 mg corn starch, 55 mg cellulose microcrystalline, 20 mg silicium dioxide anhydrous and 13 mg magnesium stearate per tablet.

Administered medications will be properly registered in KWS system.

Participants will take each OCA and placebo for 21 days across washout period at home. Drug compliance will be monitored with a daily questionnaire and subjects will state the time of taking the medication. When participant forgets to take dose at regular time, participant can still take drug until 12 hours to next dose. The bottles with the tablets will be collected after the end of each treatment period and the number of tablets will be counted and registered. With regard to medication compliance, it is not considered a deviation if the rate of taking study medication is more than 80%.

## 5.2 Drug Accountability

Participants will take medication home. The investigators will prepare blinded containers which contain the study medication to assure single blinding. Therefore, each subject's medication kit will be labelled as following:

Seulement pour les études cliniques	Alleen voor klinische studies	Nur für klinische Studien
Numéro de protocole: OCARINA Numéro EudraCT: 2020-004180-13	Protocolnummer: OCARINA EudraCT-Nummer: 2020-004180-13	Protokollnummer: OCARINA EudraCT Nummer: 2020-004180-13
Contenu: Acide obéticholique 10 mg ou placebo Conditions de stockage: 20-25°C Posologie: 1 comprimé une fois par jour le matin Utilisation orale Numéro d'identification: XX Numéro de personnage: XXXXXXXX Date d'expiration: MM / DD / YYYY	Inhoud: Obeticholzuur 10 mg of placebo Opslag condities: 20-25°C Dosering: 1 tablet 1 keer per dag in de ochtend Oral gebruik ID nummer: XX Chargenumber: XXXXXXXX Vervaldatum: MM / DD / YYYY	Inhalt: Obeticholsäure 10 mg oder Placebo Lagerbedingungen: 20-25°C Dosierung: 1 Tablette einmal täglich morgens Oraler Gebrauch ID Nummer: XX Chargenumber: XXXXXXXX Ablaufdatum: MM / DD / YYYY
Docteur: [name] [name], University of Leuven, UZ Gasthuisberg, Belgium, [contact]	Dokter: [name] [name], University of Leuven, UZ Gasthuisberg, Belgium, [contact]	Doktor: [name] [name], University of Leuven, UZ Gasthuisberg, Belgium, [contact]
Tenir hors de la portée et de la vue des enfants	Buiten het bereik en zicht van kinderen houden	Darf nicht in die Hände von Kindern gelangen

## 5.3 Concomitant / Prohibited Medication / Treatment

The following drugs must not be used 2 weeks before, during and 1 week after the study

- Drugs that can affect gastrointestinal function, motility or sensitivity or gastric acidity.
- Centrally acting medication, including antidepressants, antipsychotics and/or benzodiazepines
- Warfarin
- Proton pump inhibitors

If these drugs are taken during study medication, IMP medication will be discontinued and the subject will be excluded from the study at that time. Study data up to the time of exclusion will be available.

If these drugs are taken during the washout period, a period of at least 2 weeks should be allowed before starting the second medication.

The following drugs must not be used 1 year before, during and 1 week after the study

- Centrally acting medication, including antidepressants, antipsychotics and/or benzodiazepines (in the last year before screening visit).

If these drugs are taken during study medication, IMP medication will be discontinued and the subject will be excluded from the study at that time. Study data up to the time of exclusion will be available.

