## TRIAL FLOWCHART

### Schedule of Events – Trial specific Procedures / Assessments

Please indicate in the flowchart with different colors whether a procedure is performed as part of the standard of care or specifically for the Trial.  
Describe the visits and applicable procedures/investigations (with a reference number or letter) in more detail in a footnote below the Trial flowchart

Procedures/ Assessment	Screening	Rando- misation	Treatment Period				
			Visit 0	Visit 1	Visit 2	Visit 3	Visit 4
Visits / Contacts			0	0	0	3	3
Timing (weeks)	-30 Days to -1	-30 Days to -1	day -7 to 0	day -7 to 0	day 17 to 21	day 17 to 21	day 66 to 70
Visit Window (days)							
Informed consent	X 						
Inclusion / Exclusion criteria	X						
Demographics	X						
Medical, Surgical history	X						
Physical examination	X						
Weight / Height	X						
Vital Signs	X						
Pregnancy Test	X						
Urinalysis							
Randomisation	X						
Study drug administration 				X	X	X	X
Migrating motor complex measurement 			X		X		X
Intragastric pressure measurement 			X		X		X
Blood collection 	X			X		X	X
Duodenal aspirates 	X			X		X	X
Patient Reported Outcomes (PRO) I (questionnaire) 							
Endoscopy 				X		X	X
Duodenal biopsy 				X		X	X
Diary				X		X	X
Stool specimens 				X		X	X
(Serious) Adverse event (S/AE) assessment				X		X	X
Concomitant Medication (CM)	X	X	X	X	X	X	X

1 Enrollment and screening questionnaires: the following questionnaires will be used for screening: Patient Health Questionnaire, Dutch version of Rome IV criteria questionnaire for functional GI disorders. Enrollment and screening will be done via an online system (Quatrics).

2 Study drug administration: assignment of treatment (placebo and obeticholic acid) will be randomized before study visit 1. Either placebo or obeticholic acid will be administered orally in a single-blind fashion for 21 days. After a washout period of 28 days, either placebo or obeticholic acid will be administered as appropriate for an additional 21 days.

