7 Endoscopy: Endoscopy will be performed after a minimal fasting period of 8 hours. First, a sheathed and sealed biopsy forceps for aseptic mucosa sampling and outer diameter 1.8mm (MTW, Wesel, Germany) will be used for taking a maximum of 3 small biopsies (approximately 1 mm^2). Second, a single-use cytology brush will be used for superficial mucosal sampling. Finally, a Radial Jaw3 with needle forceps and outside diameter 2.2mm (Boston Scientific, Heredia, Costa Rica) will be used for 6 biopsies (approximately 2 mm^2) from the duodenum. All endoscopies will be performed by an experienced endoscopist. Before the procedure, local anesthetic xylocaine spray is applied in the throat with no sedation, unless demanded by subject in which case intravenous access is obtained before administration of IV Midazolam (maximum of 4mg). Aseptic biopsies (maximum 3) and brushings will be separately collected in sterile tubes, snap frozen in liquid nitrogen and stored at -80°C in the Laboratory of Molecular Bacteriology (Rega Institute) until microbial analysis. Of the conventional biopsies (n= 9 per subject per visit), 2 will be collected in RNAlater and stored at -80° in the Biobank until analysis of gene expression, 2 will be snap frozen in liquid nitrogen and stored at -80° in the Biobank until analysis of protein expression, 2 will be fixed in formalin or fixative with(-out) glutaraldehyde and stored at 4°C in the TARGID lab until later analysis of histology and 3 will be collected in ice-cold Hanks' Balanced Salt Solution (HBSS) buffer and analyzed immediately in the TARGID lab for permeability.

8 Stool samples will be collected before administration of placebo or obeticholic acid (day 0 for intervention 1, day 28 for intervention 2), after administration (day 2, 4, 7, 14, 21 for intervention 1, day 30, 32, 35, 42, 49 for intervention 2). Samples are temporarily stored by the participants in their home freezer. Within 2 weeks, samples will be brought back to UZ Leuven.

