## 7.1 Sample Size Determination

Twelve healthy volunteers will be enrolled in this placebo-controlled cross-over study. The number of volunteers to be included is calculated with a two-tailed t-test comparing two dependent means. Power calculations were based on previous results on the effect of cholestyramine (a bile acid sequestrant) on hunger sensation in healthy volunteers (23). We assume a similar effect of obeticholic acid on hunger sensation and a similar within-participant variability. We specified the following parameters: an error probability of 5%, effect size of 1.0 and a power of 80%. Based on these parameters we need to include 10 volunteers in order to highlight the expected differences. Twelve volunteers will be included to anticipate a potential dropout. Power calculations were performed with GPower version 3.0.10.

Approximately 15 participants will be screened to achieve 6 randomly assigned to Trial treatment and 6 evaluable participants for an estimated total of 12 evaluable participants per treatment group.

A maximum of 12 participants will be randomly assigned to Trial treatment such that approximately 10 evaluable participants complete the Trial.

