## 7.2 Statistical Analysis

Data from all subjects who completed the study will be included for analysis. Statistical analysis of the different parameters will be performed in SPSS for Windows (SPSS Inc., Chicago, IL, USA). Curves of whole blood glucose, plasma levels of motilin and ghrelin GLP-1, GLP-2, GIP and insulin and hunger / appetite scores over time will be analyzed using the mixed models procedure, taking into account the course of the curves over different time points. Gastric motility and BA composition will be compared with Two-tailed paired t tests or Wilcoxon signed-rank tests, depending on data distribution. Non-parametric test were applied to analyse microbiome data, with multiple testing correction whenever applicable (adjustment for false discovery rate (FDR)). Data obtained from endoscopy and gastric motility measurements prior to the start of treatment in the first part of the crossover study will be used as pre-treatment data in the second part. Results will be found significant at  $p<0.05$  significance level.

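### Section 5.3 bans benzodiazepines with no exception, yet flowchart footnote 7 offers IV midazolam at endoscopy; 5.3 needs a one-sentence exemption

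*Combined protocol and SAP*

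**What the plan says.** Section 5.3 names benzodiazepines in two prohibited lists. The first runs from 2 weeks before the study to 1 week after it, and the second from 1 year before to 1 week after. Neither list is limited by route, dose or purpose. After each list the consequence of use on treatment is mandatory: "If these drugs are taken during study medication, IMP medication will be discontinued and the subject will be excluded from the study". Section 5.3 adds "Study data up to the time of exclusion will be available". For the interval between periods it has a milder rule: "If these drugs are taken during the washout period, a period of at least 2 weeks should be allowed before starting the second medication".

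Flowchart footnote 7 describes endoscopy with throat spray and no sedation, "unless demanded by subject in which case intravenous access is obtained before administration of IV Midazolam (maximum of 4mg" being the stated limit). Midazolam is mentioned nowhere else, and section 5.4 lists no rescue medication.

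On timing, section 5.1 says "OCA and placebo will be orally administered with water in the morning for 21 days after the examinations at preintervention", and footnote 2 says "After a washout period of 28 days, either placebo or obeticholic acid will be administered as appropriate for an additional 21 days". The flowchart's visit windows are day -7 to 0, day 17 to 21 and day 66 to 70.

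On numbers, section 7.1 says "A maximum of 12 participants will be randomly assigned to Trial treatment such that approximately 10 evaluable participants complete the Trial", and section 7.2 says "Data from all subjects who completed the study will be included for analysis".

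**The concern.** A volunteer can accept something the protocol offers at one of its own procedures and, by doing so, trigger the protocol's own exclusion rule. The investigator then has two defensible but opposite courses after randomisation: remove the volunteer under 5.3, or keep the volunteer under footnote 7 contrary to the wording of 5.3. Section 9.4 does not permit planned deviations or waivers, so informally ignoring 5.3 is not a clean way out.

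The cost is greatest in period 1. A volunteer removed there never has a second-period value. Section 5.3 keeps the data already collected, but an analysis of completers does not use them, so the whole within-subject contrast is lost. Once 12 have been randomised the place cannot be refilled.

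**Working it through.** **Timing.** Period 1 dosing takes 21 days. Adding the 28-day washout puts the start of period 2 at 21 + 28 = day 49 and its end at 49 + 21 = day 70. The window of day 66 to 70 is therefore day 66 - 49 = 17 to 70 - 49 = 21 of period 2, which matches day 17 to 21 of period 1. Both post-baseline windows fall in dosing. Two cautions apply. The flowchart columns are damaged in the text available, so the exact endoscopy columns are uncertain, although every post-baseline window shown is on treatment. Footnote 8 dates the second intervention from day 28, which does not fit a 28-day washout after 21 days of dosing. Day 49 is the better reading, and the period 1 argument does not depend on it.

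**What 5.3 does to a volunteer given midazolam:**

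| Endoscopy | Result under 5.3 read literally |
|---|---|
| Baseline, day -7 to 0 | Breaches the ban, but precedes study medication, so the exclusion sentence is not triggered |
| Day 17 to 21, still dosing | IMP stopped, volunteer excluded, no period 2 |
| Day 21, after the last tablet | The washout rule arguably applies; 28 days exceeds the 2 weeks required, so no exclusion |
| Day 66 to 70, still dosing | Excluded, but both periods' appetite data may already exist; completer status unclear |

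**The plan's sample size.** Inputs from section 7.1: two-sided paired t-test, alpha 0.05, effect size d = 1.0, power 80%, 10 needed, 12 enrolled. Power for n completers is P(|T| > t(0.975, n-1)), where T is noncentral t with n - 1 degrees of freedom and noncentrality d x sqrt(n).

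| Completers n | d x sqrt(n) | Critical t | Power |
|---|---|---|---|
| 12 | 3.464 | 2.201 | 0.883 |
| 11 | 3.317 | 2.228 | 0.848 |
| 10 | 3.162 | 2.262 | 0.803 |
| 9 | 3.000 | 2.306 | 0.748 |

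The smallest n reaching 0.80 is 10, so the plan's figure reproduces. The reserve is 12 - 10 = 2 volunteers.

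**Size of the loss.** The documents give no sedation rate. Let q be the assumed share of volunteers sedated and excluded in period 1, with losses Binomial(12, q) and no other dropout. The chance of at least one exclusion is 1 - (1 - q)^12. Mean power averages the power at each number of completers over that binomial distribution.

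| q (assumed) | P(at least 1 lost) | P(3 or more lost) | Mean power |
|---|---|---|---|
| 5% | 0.460 | 0.020 | 0.860 |
| 10% | 0.718 | 0.111 | 0.834 |
| 15% | 0.858 | 0.264 | 0.805 |
| 20% | 0.931 | 0.442 | 0.771 |
| 30% | 0.986 | 0.747 | 0.694 |

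Mean power reaches 0.80 at q of about 15.7%. These figures use the plan's paired t-test, not the mixed model named for the primary endpoint. If footnote 7 controls, every loss in the table is zero.

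**The case against.** The strongest reply is that a specific provision usually governs a general one. Section 5.3 is a general restriction on concomitant medication. Footnote 7 is a dose-capped step given by staff within a protocol procedure. Read literally, 5.3 would bar midazolam at every endoscopy and leave footnote 7 almost nothing to do, so the investigator would probably not apply it that way. The word taken in 5.3 also suits participants' own medication. This is a sensible guess at intent and stands as such. However, the prohibition itself is worded in terms of use, which covers drugs given by staff, and nothing ranks one provision above the other.

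A second reply is that the reserve of two covers low uptake and that sedation is not the default. This stands.

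Three stronger readings are tempting, and the documents do not support them:
- A reader might infer that the trial will fall below 80% power. That needs at least three exclusions, or an average uptake above about 16% with every sedated volunteer excluded, and no rate is stated.
- A reader might infer that sedation will contaminate the appetite scores. As far as the flowchart can be read, the motility and intragastric pressure tests, where appetite is scored, are at visits 0, 2 and 4, and endoscopy is at visits 1, 3 and a later visit. The order already appears to put appetite testing first.
- A reader might infer divergent handling across sites. The synopsis names one centre, so one clarification settles the practice.

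**Conclusion.** Wrong as written, minor severity. Section 5.3 and footnote 7 conflict, and nothing in the documents reconciles them. Followed literally, 5.3 drops from a completer-only crossover of at most 12 volunteers anyone sedated while dosing in period 1, and sedation at the baseline endoscopy breaches the ban as well.

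The size depends on two things the documents leave open: how many volunteers ask for sedation, and which provision the investigator follows. If footnote 7 is followed, no volunteer is lost. If 5.3 is followed, one or two exclusions remain inside the planned reserve, and the third takes power at d = 1.0 below target, before any other dropout. The case for correcting the text does not rest on high uptake, because a single sedated volunteer is enough to force the choice.

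**What to change.** Add one sentence to section 5.3: a single procedural dose of IV midazolam (maximum 4 mg) given under flowchart footnote 7, at the baseline or an on-treatment endoscopy, is permitted under both prohibited lists, is recorded as concomitant medication with dose and time, and does not lead to IMP discontinuation or exclusion.

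No new scheduling rule is needed beyond keeping the present visit order, with motility, intragastric pressure and appetite testing before endoscopy in each window. The concomitant-medication row is already marked at every visit, so recording adds only the dose and time.

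The cost is one sentence, with no extra visits or participants and no change to the 10 needed or 12 enrolled. The downside is that some duodenal samples will be taken under midazolam. These should be flagged in the analysis from the recorded dose.
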